#### 9.15.2 Clinical Laboratory Evaluations

Descriptive statistics for chemistry, hematology, coagulation, urinalysis, eGFR (categorized as chemistry), and serum testosterone and the change from baseline will be summarized for the Safety Analysis Set at each scheduled time point.

Laboratory values will be categorized into normal or higher or lower than the normal range. Laboratory values will be presented in standard international (SI) units. Number and percent of participants with abnormal laboratory values will be summarized by timepoint. Shift tables based on CTCAE v5.0 toxicity grading as shown in Appendix 2 will be provided for shifts from baseline to the highest and lowest post-baseline grade. Shift tables will be presented for hematology, chemistry, coagulation, and urinalysis parameters as applicable.

Listings will be provided by participant and study visit. Values for all safety laboratory results that are outside the laboratory reference ranges will be flagged on the individual patient data listings as high or low. Additionally, listings of abnormal laboratory values will be provided.

#### 9.15.3 Vital Signs

Systolic and diastolic blood pressures (mmHg), heart rate (bpm), respiratory rate (breaths/minute), and temperature (°C), as well as height, weight, and BMI, will be summarized using descriptive statistics at all scheduled time points. Descriptive statistics of the change from baseline to each post-baseline time point will also be provided.

#### 9.15.4 Electrocardiogram (ECG) Parameters

Duplicate 12-lead ECGs will be captured pre-dose and post-dose on Day 0 along with abnormal finding and clinical interpretations. The mean of the duplicate ECG values will be calculated, presented in listings used for change from baseline calculations.

The values of the ECG parameters: RR interval, PR interval, QRS interval, QT interval, QTcB, and QTcF interval will be summarized using descriptive statistics at all scheduled time points as well as changes from baseline. Shift tables will be provided for changes from baseline using the categories of normal, abnormal but not clinically significant, and abnormal and clinically

September 4, 2024 CONFIDENTIAL Page 38 of 46

significant. For duplicate readings at a single timepoint, the result with the greatest clinical significance will be used for the shift table category assignment.

The number and percentages of participants with QTcF and QTcB values that fall into the following categories post-baseline will also be summarized:

- < 450 msec
- > 450 and  $\le 480$  msec
- > 480 and < 500
- $\bullet$  > 500 msec

In addition, the number and percentage of participants with the following post-baseline increases in QTcF and QTcB will be summarized:

- <0 msec
- 0 30 msec
- > 30-60 msec
- > 60 msec

A listing of ECG data will also be provided and will include the overall tracing assessment of normal, abnormal and clinically significant status for these measurements.

## 9.15.5 Physical Examination

Physical examination findings will be listed by body system. Abnormal findings will be described.

## 9.15.6 Prostate Cancer Symptoms

PC symptoms will be summarized by body system, symptom, and severity grade for the Safety Analysis Set. Locations of symptoms will also be summarized.

All PC symptom data will be listed.

#### 9.16 Biodistribution Analysis

For the Biodistribution Analysis Set, biodistribution measures for Cu-SAR-bisPSMA of mean and max SUV, lesion longest diameter, lesion longest perpendicular, lesion-to-background ratios (SUVr), and reader confidence levels will be summarized descriptively. Mean and max SUV will use the mean of all lesions within a participant to summarize SUV in all lesions, and separately will summarize mean and max SUV in lesions in visceral/soft tissues and lesions in bone. Similarly, lesion-to-background ratio will use the mean values of the lesions within a participant. Boxplots will be provided for the biodistribution measures.

September 4, 2024 CONFIDENTIAL Page 39 of 46

Additional summaries the of biodistribution measures above will be provided for the following subgroups:

- Participants who were TP for the primary analysis at the participant-level
- Participants who were FP for the primary analysis at the participant-level

All individual, mean and max SUV, and SUVr measurements in organ, all lesions, visceral/soft tissue lesions, and bone lesions will be listed for each participant without being combined or averaged and will also include the value averaged over all lesions within participant that is used in the summaries. Reader confidence levels will also be listed.

September 4, 2024 CONFIDENTIAL Page 40 of 46

**APPENDICES Appendix 1 Schedule of Events** 

	Screening 	 Cu-	-SAR-bisPS	SMA PET/CT	Safety Visit	Follo	ow-Up
Study Days	28 days	Da	y 0	Day 1	Day 7 (±2 days)	Day 90 (±15 days)	Day 180 (±15 days)
Visit	1		2	3	4	5	62
Timeline		Pre Dose	Post Dose	24h (±6h) Post Dose			
Informed Consent 	X						
Inclusion/Exclusion	X						
Demographics and Disease Characteristics 	X						
Medical and Medication History 	X						
Prior Cancer Treatments	X						
Prostate Cancer Treatments					X	X	X
Physical Exam 		X			X		
Body Weight	X	X			X		
Height	X						
ECOG Status 	X						
Vital Signs 		X	$X^9$		X		
Duplicate 12-Lead ECG		X	$X^{10}$				
Hematology 	X				X		
Biochemistry 	X				X		
Coagulation 	X				X		
eGFR (CKD-EPI) in mL/min	X				X		
Serum Testosterone	X						
Urinalysis 		X			X		
Total PSA 	X					X	X
AEs	X	X	X	X	X		
Concomitant Medications	X	X	X	X	X		
 Cu-SAR-bisPSMA Dose			X				
 Cu-SAR-bisPSMA PET/CT			$X^{16}$	$X^{17}$			
SOC Conventional Scan	X						
Follow-up Conventional Imaging 						X	X
Additional Imaging/Histopathology 						X	

September 4, 2024 CONFIDENTIAL Page 41 of 46

# CLARITY PHARMACEUTICALS LTD Study Drug: 64Cu-SAR-bisPSMA

## Protocol: CLP06 Statistical Analysis Plan, Version 1.0

Disease Management Form	$X^{20}$		$X^{21}$	

<sup>1 Results of SOC tests or examinations performed prior to obtaining informed consent and within 28 days prior to Day 0 may be used; such tests do not need to be repeated for Screening. Institutional SOC scan(s) must be performed within 60 days of Day 0. SOC scan(s) performed more than 60 days prior to Day 0 may be repeated as a study screening procedure and reviewed by the Investigator prior to Day 0.

 PET/CT scan to be performed at 1 to 4 hours post Cu-SAR-bisPSMA administration. If no anatomical imaging (CT or MRI) is available within 60 days of Day 0, a diagnostic quality CT must be acquired as part of the Day 0 PET/CT scan.

September 4, 2024 CONFIDENTIAL Page 42 of 46

<sup>2 Visit 6 is only applicable to participants who were deemed negative or equivocal for PC recurrence based on the Visit 5 follow-up conventional imaging (as per the central expert panel's interpretation).

<sup>3 Informed consent must be documented before any study-specific screening procedure is performed and may be obtained more than 28 days before the Cu-SAR-bisPSMA administration.

<sup>4 Demographic data include: year of birth, race, ethnicity. Baseline disease characteristics include: initial diagnosis stage (per American Joint Committee on Cancer), initial Gleason score, initial diagnosis stage (T, N and M staging), pathology results, date of biochemical recurrence, relevant symptom history including, gastrointestinal, genitourinary and musculoskeletal.

<sup>5 Medical history will include evaluation of: relevant past or present diseases or disorders, and relevant surgical history. Medication history within 14 days before signing informed consent should be collected.

<sup>6 Physical examination includes assessment of: general appearance, cardiovascular system, respiratory system, and nervous system if vertebral involvement.

<sup>7 ECOG Scale is used by the Investigator to determine the score (0 to 5) that best represents the participants' activity status.

<sup>8 Vital signs include: body temperature, respiratory rate, heart rate and systolic and diastolic blood pressure.

<sup>9 Post-dose vital signs to be completed prior to the Cu-SAR-bisPSMA PET/CT.

<sup>10 Post-dose ECG to be performed at 30 minutes (±10 minutes) post Cu-SAR-bisPSMA administration.

<sup>11 Hematology: hemoglobin, hematocrit, red blood cell count, WBC, platelet count, differential WBC (neutrophils, eosinophils, basophils, lymphocytes, and monocytes), absolute neutrophil count, and absolute lymphocyte count.

12 <u>Biochemistry (pre-prandial): albumin, total protein, blood glucose, sodium, potassium, blood urea nitrogen, creatinine, calcium, uric acid, AST, ALT, total bilirubin, alkaline phosphatase.

 $^{13}$  Coagulation: prothrombin time, activated partial thromboplastin time, D-dimer.

<sup>14 Urinalysis to include determination of protein, glucose and leukocytes (dipstick test).

<sup>15 If radiation or other salvage focal therapy is initiated during the study, PSA levels will be monitored independent of the study visit schedule at every 4 weeks ( $\pm 2$  days) from the initiation of the therapy. PSA response (defined as total PSA decline by ≥50% from baseline) must be confirmed by a second value within 4 weeks.

 $^{17}$  PET/CT scan to be performed at 24 hours ( $\pm 6$  hours) post  $^{64}$ Cu-SAR-bisPSMA administration.

<sup>18 Follow-up conventional imaging will include MRI or CT (a diagnostic quality CT completed as part of a PET/CT scan is acceptable) and 99mTc-MDP and/or F-fluciclovine and/or C-choline and/or approved PSMA PET (such as F-DCFPyL or Ga-PSMA-11). *Note: Additional follow-up conventional imaging may be completed at any other timepoint, as deemed appropriate by the Investigator. All follow-up scans acquired within 180 days* (±15 days) of Day 0 must be transferred to the central reading center.

## Protocol: CLP06 Statistical Analysis Plan, Version 1.0

September 4, 2024 CONFIDENTIAL Page 43 of 46

<sup>19 Additional follow-up conventional imaging may be performed at the discretion of the Investigator. Where feasible, obtaining histopathology from biopsy or surgery should be attempted for as many Cu-SAR-bisPSMA PET-positive lesions as possible (based on the local interpretation of the Cu-SAR-bisPSMA PET/CT scans). If clinically feasible, the Investigator should make every effort to obtain histopathology for at least one Cu-SAR-bisPSMA PET-positive lesion **per region**. All follow-up scans and histopathology acquired within 180 days (±15 days) of Day 0 must be transferred to the central reading center.

<sup>20 Pre-SAR-bisPSMA Disease Management Form must be completed by the treating physician to document the initial intended management plan for the participant based on available clinical information and conventional imaging results.

<sup>21 Post-SAR-bisPSMA Disease Management Form must be completed by the treating physician for all participants who complete the Cu-SAR-bisPSMA PET/CT scan(s). The management plan will be based on the result from the local interpretation of the Cu-SAR-bisPSMA PET/CT scan(s) to document whether a change to the initial intended management plan may be warranted due to the Cu-SAR-bisPSMA PET/CT finding(s).

## **Appendix 2 Programmatic CTCAE v5.0 Toxicity Grading**

Laboratory Test/Vital Sign	Grade 1	Grade 2	Grade 3	Grade 4			
Chemistry							
(Albumin)	<LLN $- 3$ g/dL;	<3-2 g/dL;	<2 g/dL;				
Hypoalbuminemia	<lln 30="" g="" l<="" td="" –=""><30-20 g/L	<20 g/L		</lln>	<30-20 g/L	<20 g/L				
Alkaline phosphatase increased	>ULN – 2.5 x ULN if baseline was normal;	>2.5 – 5.0 x ULN if baseline was normal;	>5.0 – 20.0 x ULN if baseline was normal;	>20.0 x ULN if baseline was normal;			
	2.0-2.5 x baseline if baseline was abnormal	>2.5-5.0 x baseline if baseline was abnormal	>5.0-20.0 x baseline if baseline was abnormal	>20.0 x baseline if baseline was abnormal			
Alanine aminotransferase (ALT) increased	>ULN – 3 x ULN if baseline was normal;	>3.0 – 5.0 x ULN if baseline was normal;	>5.0 – 20.0 x ULN if baseline was normal;	>20.0 x ULN if baseline was normal;			
	1.5-3.0 x baseline if baseline was abnormal	>3.0-5.0 x baseline if baseline was abnormal	>5.0-20.0 x baseline if baseline was abnormal	>20.0 x baseline if baseline was abnormal			
Aspartate aminotransferase (AST) increased	>ULN – 3 x ULN if baseline was normal;	>3.0 – 5.0 x ULN if baseline was normal;	>5.0 – 20.0 x ULN if baseline was normal;	>20.0 x ULN if baseline was normal;			
	1.5-3.0 x baseline if baseline was abnormal	>3.0-5.0 x baseline if baseline was abnormal	>5.0-20.0 x baseline if baseline was abnormal	>20.0 x baseline if baseline was abnormal			
(Calcium high,	>ULN – 11.5 mg/dL;	>11.5 – 12.5 mg/dL;	>12.5 – 13.5 mg/dL;	>13.5 mg/dL;			
corrected) Hypercalcemia	>ULN – 2.0 mmol/L	>2.9 – 3.1 mmol/L	>3.1 – 3.4 mmol/L	>3.4 mmol/L;			
(Calcium low,	<lln 8.0="" dl;<="" mg="" td="" –=""><8.0 – 7.0 mg/dL;	<7.0 – 6.0 mg/dL;	<6.0 mg/dL;	</lln>	<8.0 – 7.0 mg/dL;	<7.0 – 6.0 mg/dL;	<6.0 mg/dL;			
corrected)	<lln 2.0="" l<="" mmol="" td="" –=""><2.0 – 1.75 mmol/L	<1.75 – 1.5 mmol/L	<1.5 mmol/L	</lln>	<2.0 – 1.75 mmol/L	<1.75 – 1.5 mmol/L	<1.5 mmol/L			
Hypocalcemia			Hospitalization	Life-threatening			

September 4, 2024 CONFIDENTIAL Page 44 of 46

## Protocol: CLP06 Statistical Analysis Plan, Version 1.0

Laboratory Test/Vital Sign	Grade 1	Grade 2	Grade 3	Grade 4		
Creatinine Increased	>ULN – 1.5 ULN	>1.5-3.0 x baseline	>3.0 x baseline	>6.0 x ULN		
		>1.5-3.0 x ULN	>3.0-6.0 x ULN			
(eGFR or Creatinine Clearance)	eGFR or CrCL < LLN - 60 ml/min/1.73 m2	eGFR or CrCl 59 – 30 ml/min/1.73 m2	eGFR or CrCl 29 -15 ml/min/1.73 m2	eGFR or CrCl < 15 ml/min/1.73 m2		
Chronic Kidney Disease						
(Glucose)	<lln 55="" dl;<="" mg="" td="" –=""><55 – 40 mg/dL;	<40 – 30 mg/dL;	<30 mg/dL;	</lln>	<55 – 40 mg/dL;	<40 – 30 mg/dL;	<30 mg/dL;		
Hypoglycemia	<lln 3.0="" l<="" mmol="" td="" –=""><3.0 – 2.2 mmom/L	<2.2 – 1.7 mmol/L	<1.7 mmol/L;	</lln>	<3.0 – 2.2 mmom/L	<2.2 – 1.7 mmol/L	<1.7 mmol/L;		
				Life-threatening		
(Potassium high) Hyperkalemia	>ULN – 5.5 mmol/L	>5.5 - 6.0 mmol/L; intervention initiated	>6.0-7.0 mmol/L; Hospitalization	>7.0 mmol/L; Life-threatening		
(Potassium low) Hypokalemia		<lln 3.0="" l<="" mmol="" td="" –=""><3.0 – 2.5 mmol/L; Hospitalization	<2.5 mmol/L; Life-threatening	</lln>	<3.0 – 2.5 mmol/L; Hospitalization	<2.5 mmol/L; Life-threatening		
(Sodium high) Hypernatremia	>ULN – 150 mmol/L	>150-155 mmol/L	>155-160 mmol/L; Hospitalization	>160 mmol/L; Life-threatening		
(Sodium low)	<lln 130="" l<="" mmol="" td="" –="">125-129 mmol/L	120-124 mmol/L	<120 mmol/L	</lln>	125-129 mmol/L	120-124 mmol/L	<120 mmol/L		
Hyponatremia						
Total bilirubin increased	>ULN – 1.5 x ULN if baseline was normal;	>1.5 – 3.0 x ULN if baseline was normal;	>3.0 – 10.0 x ULN if baseline was normal;	>10.0 x ULN if baseline was normal;		
	1.0-1.5 x baseline if baseline was abnormal	>1.5-3.0 x baseline if baseline was abnormal	>3.0-10.0 x baseline if baseline was abnormal	>10.0 x baseline if baseline was abnormal		
Hematology						
Hemoglobin increased	Increase in >0-2 g/dL	Increase in >2-4 g/dL	Increase in >4 g/dL			
(Hemoglobin low)	<lln 10.0="" dl<="" g="" td="" –=""><10.0-8.0 g/dL	<8.0 g/dL		</lln>	<10.0-8.0 g/dL	<8.0 g/dL			

September 4, 2024 CONFIDENTIAL Page 45 of 46

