10.4.4.2 Laboratory Data Analysis

Safety laboratory parameters and corresponding changes from baseline will be presented as descriptive statistics by visit. Shift tables based on the NCI-CTCAE v5.0 toxicity grading will be presented for selected laboratory parameter between baseline and the highest/lowest post-baseline NCI-CTCAE v5.0 toxicity grade. Any clinically significant abnormalities in laboratory values will be listed.

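### The hemoglobin-increased row in SAP Appendix 2 has no stated reference point and no normal-range condition, so on the natural reading chance rises appear as Grade 1 shifts in a descriptive safety table

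*SAP*

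**What the plan says.** SAP Appendix 2, which is headed as programmatic CTCAE v5.0 grading, gives three bands for increased hemoglobin. Grade 1 is "Increase in >0-2 g/dL", Grade 2 is "Increase in >2-4 g/dL", and Grade 3 is any increase above 4 g/dL. The row mentions neither ULN nor the participant's baseline status, and it does not name the value from which the increase is counted.

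Most other high-direction rows are anchored. Grade 1 for high potassium, for example, is ">ULN – 5.5 mmol/L". The liver and alkaline phosphatase rows start above ULN when baseline was normal and use a multiple of baseline only under a condition, as in "2.0-2.5 x baseline if baseline was abnormal".

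SAP 9.15.2 puts the appendix to use: "Shift tables based on CTCAE v5.0 toxicity grading as shown in Appendix 2 will be provided", running from baseline to the highest and lowest post-baseline grade. It then adds: "Shift tables will be presented for hematology, chemistry, coagulation, and urinalysis parameters as applicable". Protocol 10.4.4.2 is looser; its shift tables "will be presented for selected laboratory parameter between baseline and the highest/lowest post-baseline" grade, without naming the parameters.

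Hemoglobin is part of the hematology panel (Protocol 7.2.6). The schedule has hematology at Screening and at the Day 7 Safety Visit (Protocol Table 5; SAP Appendix 1). Baseline is the last non-missing value before dosing (SAP 7.1.1).

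**The concern.** A row that is triggered by any movement above zero, in a table of shifts from baseline, measures the sign of a difference between two readings. If the increase is counted from baseline, no participant can hold the grade at baseline, so every positive difference becomes a new post-dose shift. This holds even when both values are normal.

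The study has one arm, so no control column would show the reader that such shifts are what repeat measurement produces. The table could report post-dose Grade 1 hemoglobin increases in a large minority of participants when nothing has happened, and the few values truly above the normal range would sit among them unmarked. At stake is how one safety table reads.

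**Working it through.** **Plan's own figure.** Neither document gives an expected frequency of hemoglobin shifts, so there is none to reproduce.

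**Inputs from the documents**
- Grade 1 trigger: increase above 0 g/dL (SAP Appendix 2).
- One scheduled baseline and one scheduled post-dose hematology sample (Protocol Table 5).
- About 50 participants (SAP 4.2).

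**Assumptions, not in the documents**
- The increase is counted from baseline.
- Results are reported to 0.1 g/dL.
- The Day 7 minus Screening difference is normal with mean μ and SD σ, where σ is 0.3 to 0.7 g/dL. There is no drug effect: μ = 0, or μ = −0.1 g/dL for an assumed small mean fall.

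**Formula.** A rise is recorded when the rounded difference is at least 0.1 g/dL, that is, when the unrounded difference is at least 0.05:

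P(Grade 1 or higher) = 1 − Φ((0.05 − μ)/σ)

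For example, with μ = 0 and σ = 0.3: 1 − Φ(0.05/0.3) = 1 − Φ(0.167) = 0.434. With μ = −0.1 and σ = 0.3: 1 − Φ(0.15/0.3) = 1 − Φ(0.5) = 0.309.

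| σ (g/dL) | μ = 0 | of 50 | μ = −0.1 | of 50 |
|---|---|---|---|---|
| 0.3 | 0.434 | 22 | 0.309 | 15 |
| 0.5 | 0.460 | 23 | 0.382 | 19 |
| 0.7 | 0.472 | 24 | 0.415 | 21 |

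**Cross-check by simulation.** One million pairs of readings were drawn, each reading rounded to 0.1 g/dL. A within-person SD of 0.2 to 0.5 g/dL corresponds to σ = √2 × SD, or 0.28 to 0.71 g/dL. With no drift the rate is 43.1% to 47.1%; with a mean fall of 0.1 g/dL it is 29.9% to 41.6%. A mean rise of 0.1 g/dL moves it to between 52.8% and 56.9%. Nearly all of this is Grade 1: with no drift, a rise above 2 g/dL occurs in at most 0.2% over this SD range.

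**How much lies inside the normal range.** With a further assumed hemoglobin distribution (mean 14, between-person SD 1.2 g/dL) and an assumed normal range of 13.0 to 17.5 g/dL, about 33% to 34% of all participants would have a rise with both values normal.

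**With a ULN condition.** The same simulation, with the increase counted above the larger of ULN (17.5, assumed) and baseline, gives 0.10% to 0.25%. That is 50 × 0.0010 = 0.05 to 50 × 0.0025 = 0.13 participants. Even at a within-person SD of 1.0 g/dL the rate is about 1%.

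**The case against.** The strongest reply is that the row never says the increase is from baseline. If the programmer takes it as an increase above ULN, the effect disappears. That is correct, and it limits the claim: the defect on the page is a missing reference point and a missing range condition, and the any-rise rule is an inference. The inference is the natural one, because the row speaks of an increase and the tables it feeds are shifts from baseline.

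A second reply is that the appendix is meant to carry CTCAE v5.0, which Protocol 10.4.4.2 names. Whether the printed row reproduces that scale cannot be checked from the two documents. If it does, adding a condition departs from the named grading. This also stands, and it is why the change has to be disclosed.

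Third, the row may never be tabulated: SAP 9.15.2 limits the shift tables to what is applicable, and the protocol to selected parameters. Neither excludes hemoglobin, though, and the appendix lists it.

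Fourth, the anchoring of the appendix is not uniform. High lymphocytes use fixed counts, and creatinine Grades 2 and 3 include baseline multiples with no range condition. So hemoglobin differs from most high-direction rows, not from all of them. Its trigger of any change above zero is still far lower than theirs.

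A reader might also infer that the row distorts the primary safety result, or hides a true hemoglobin signal. The documents do not support either inference. The primary safety endpoint is the incidence and severity of treatment-emergent and serious adverse events (SAP 3.1.1), and a laboratory value becomes an adverse event only if judged clinically significant (Protocol 7.2.6 and 9.1). A fall in hemoglobin has its own row anchored at the lower limit of normal. SAP 9.15.2 also provides change from baseline, counts of abnormal values by timepoint, and flagged listings, so a real rise or fall would be visible there.

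**Conclusion.** The point holds as a minor one. As printed, the row leaves its reference point open, and nothing else in either document restricts it to abnormal values. On the change-from-baseline reading, about 43% to 47% of participants (22 to 24 of 50) would show a Grade 1 or higher shift with no drug effect, and 31% to 42% (15 to 21 of 50) with a mean fall of 0.1 g/dL.

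These figures rest on the assumed SD, symmetry and 0.1 g/dL reporting. With no drift the rate depends little on the SD, because the threshold is close to zero; it depends more on drift. A flat statement that half of participants will be graded would therefore go too far. Unscheduled repeat samples would push the rate up, because the highest post-baseline grade is used.

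The consequence is confined to a descriptive shift table that could be misread.

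**What to change.** Program the row so that a grade is assigned only when the post-baseline value is above ULN. Measure the increase from ULN, or from baseline if baseline is already above ULN. Keep the printed bands (above 0 to 2, above 2 to 4, above 4 g/dL). A value at or below ULN gets no hemoglobin-increased grade.

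Footnote the shift table and Appendix 2 to say that this range condition was added to the printed grading, so that a table labelled CTCAE v5.0 does not carry an undisclosed change.

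The cost is one table row, its program and a footnote. The downside is that the row no longer follows the printed grading literally. No data collection changes, and no other row is affected.

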## Protocol: CLP06 Statistical Analysis Plan, Version 1.0

Laboratory Test/Vital Sign	Grade 1	Grade 2	Grade 3	Grade 4		
Anemia	<lln 6.2="" l<="" mmol="" td="" –=""><6.2-4.9 mmol/L	<4.9 mmol/L		</lln>	<6.2-4.9 mmol/L	<4.9 mmol/L			
	<lln 100="" g="" l<="" td="" –=""><100-80 g/L	<80 g/L		</lln>	<100-80 g/L	<80 g/L			
Lymphocyte count	<lln 800="" mm3<="" td="" –=""><800-500/mm3	<500-200/mm3	<200/mm3	</lln>	<800-500/mm3	<500-200/mm3	<200/mm3		
decreased	<lln 0.8="" 10^9="" l<="" td="" x="" –=""><0.8-0.5 x 10^9/L	<0.5-0.2 x 10^9/L	<0.2 x 10^9/L	</lln>	<0.8-0.5 x 10^9/L	<0.5-0.2 x 10^9/L	<0.2 x 10^9/L		
Lymphocyte count increased		>4000/mm3- 20,000/mm3	>20,000/mm3			
Neutrophil count	<lln 1500="" mm3<="" td="" –=""><1500 - 1000/mm3	<1000 - 500/mm3	<500/mm3	</lln>	<1500 - 1000/mm3	<1000 - 500/mm3	<500/mm3		
decreased	<lln 1.5="" 10^9="" l<="" td="" x="" –=""><1.5-1.0 x 10^9/L	<1.0-0.5 x 10^9/L	<0.5 x 10^9/L	</lln>	<1.5-1.0 x 10^9/L	<1.0-0.5 x 10^9/L	<0.5 x 10^9/L		
Platelet count decreased	<lln 75,000="" mm3<="" td="" –=""><75,000 - 50,000/mm3	<50,000 - 25,000/mm3	<25,000/mm3	</lln>	<75,000 - 50,000/mm3	<50,000 - 25,000/mm3	<25,000/mm3		
	<lln 10^9="" 75.0="" l<="" td="" x="" –=""><75.0-50.0 x 10^9/L	<50.0 – 25.0 x 10^9/L	<25.0 x 10^9/L	</lln>	<75.0-50.0 x 10^9/L	<50.0 – 25.0 x 10^9/L	<25.0 x 10^9/L		
WBC Count decreased	<lln 3000="" mm3<="" td="" –=""><3000-2000/mm3	<2000-1000/mm3	<1000/mm3	</lln>	<3000-2000/mm3	<2000-1000/mm3	<1000/mm3		
	<lln-3.0 10^9="" l<="" td="" x=""><3.0-2.0 x 10^9/L	<2.0-1.0 x 10^9/L	<1.0 x 10^9/L	</lln-3.0>	<3.0-2.0 x 10^9/L	<2.0-1.0 x 10^9/L	<1.0 x 10^9/L		
Coagulation						
aPTT/PTT prolonged	>ULN – 1.5 x ULN	>1.5 – 2.5 x ULN	>2.5 x ULN			
Urinalysis						
(Protein high)	1+ proteinuria;	2+ and 3+ proteinuria;	4+ proteinuria;			
Proteinuria	Urinary protein ≥ULN - <1.0 g/24 hrs	Urinary protein 1.0 - <3.5 g/24 hrs;	Urinary protein >=3.5 g/24 hrs;			

September 4, 2024 CONFIDENTIAL Page 46 of 46
